### **8.2.4 Seizure Status**

The seizure diary (see Section 8.1.3) will be provided to caregivers for completion at home after initial training at the clinic. The *diary* entries are event driven, i.e., have to be completed *retrospectively* after a seizure occurred, and contain information on seizure type, duration, and frequency based on guidance from the International League Against Epilepsy (ILAE; Scheffer et al 2017, Fisher et al 2017). A *list of seizure types is provided for selection by the Investigator based on the "ILAE 2017 Classification of Seizure Types Expanded Version"* (Appendix 7) to support the seizure diary entries.

In addition, the seizure diary asks to confirm accurate entries at regular intervals.

The Investigator will determine the participant's recent seizure status at the timepoints specified in the SoA (*in Part 1 and for the first 6 months in Part 2; see Section 1.3*), based on caregiver report (time since last visit) and review of the information in the seizure diary (see Table 11 for review period for each assessment).

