**Table 1 Schedule of Activities for Part 1 – Overview**

Period	Screening a	Baseline b	Treatment Period/Visit							Final Visit	Follow-up c, q	Early Termination c
Day	Day -35 to Day -2	Day -7 to Day -1	Day 1	Day 2	Day 14	Day 28 d	Day 92 c	Day 183 b	Day 274 c	Day 365 b	Day 395	Anytime
Weeks (approximate)	Week -5 to Week -1	Week -1	Week 1	Week 1	Week 2	Week 4	Week 14	Week 26	Week 40	Week 52	Week 56	
Visit window					± 5 days	± 5 days	± 7 days	± 7 days	± 7 days	± 7 days	± 10 days	
Assessments												
Informed consent	x									x t		
Inclusion/Exclusion criteria	x	x										
Caregiver expectation guidance u	x	x						x		x		
Randomization		x										
Demography	x											
Medical history	x											
Physical examination e	x	x						x		x		
Assessment of hypotonia		x		x	x			x		x		
Vital signs	x	x	x	x	x		x	x	x	x q	x	x
Genetic test : CMA r	x											
Genetic test : MS-MLPA r	x											
Genetic test: FISH r					x							
Pregnancy test f	x	x					x	x	x	x q	x	x
Urinalysis	x	x			x		x	x	x	x q	x	x
Hematology	x	x			x		x	x	x	x q	x	x
Clinical chemistry	x	x			x		x	x	x	x q	x	x
Coagulation	x											
Viral serology	x											
Thyroid hormones	x									x q		
RBR whole blood sample (optional)		x										
Tanner staging g		x								x		
12-lead ECG (triplicate)	x	x	x	x	x			x		x q		
Seizure status h		x				x	x	x	x	x	x	x
EEG monitoring i		x	x	x	x			x		x q		
Study drug administration j			◀							▶		
PK sample k			x	x	x		x	x	x	x q		x
Dup15q CGI-S h	x	x				x	x	x	x	x	x	x
Dup15q CGI-C h						x	x	x	x	x	x	x

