**Table 1 Schedule of Activities for Part 1 – Overview (cont.)**

Period	Screening a	Baseline b	Treatment Period/Visit							Final Visit	Follow-up c, q	Early Termination c
Day	Day -35 to Day -2	Day -7 to Day -1	Day 1	Day 2	Day 14	Day 28 d	Day 92 c	Day 183 b	Day 274 c	Day 365 b	Day 395	Anytime
Weeks (approximate)	Week -5 to Week -1	Week -1	Week 1	Week 1	Week 2	Week 4	Week 14	Week 26	Week 40	Week 52	Week 56	
Visit window					± 5 days	± 5 days	± 7 days	± 7 days	± 7 days	± 7 days	± 10 days	
Assessments												
VINELAND-3 i		x						x		x		x
MSEL m		x						x		x		
RBS-R n		x					x	x	x	x		x
ADOS m		x									x	
PedsQL-FIM n		x						x		x		
ORCA n		x						x		x		x
ABC-2-C n		x				x	x	x	x	x		x
Dup15q CaGI-S n		x			x	x	x	x	x	x	x	x
Dup15q CaGI-C n					x	x	x	x	x	x	x	x
CSHQ n		x			x	x	x	x	x	x		x
Clinical assessment of suicidality h, o	x	x		x		x	x	x	x	x	x	x
Wearable device p	x					x	x	x	x	x		
Seizure diary	◀									▶		
Palatability questionnaire			x		x							
Meal record			x	x	x		x	x	x	x		
Drug diary			◀							▶		
Exit interview (optional) s											x	
Adverse events	◀											▶
Previous and concomitant treatments	◀											▶

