Based on the eligibility criteria for this study protocol, and the measures that will be implemented to monitor participant safety (e.g., guidance regarding prohibited therapy [including CYP3A4 inhibitors/inducers], safety monitoring throughout the treatment period and follow-up period [laboratory tests, ECG, seizure status, and EEG], implementation of PK monitoring with dose adjustment, age-staggered approach for inclusion, implementation of dosing stopping rules at the individual participant level, and implementation of a Sponsor Internal Monitoring Committee [IMC] and Scientific Oversight Committee [SOC]), the risk to participants with Dup15q syndrome treated with basmisanil is considered small and will be re-evaluated on an ongoing basis.

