### **8.1.3.2 Devices**

To access the dedicated website (*TrialMax*) (Section 8.1.3.1) for diary entries or completion of caregiver-reported assessments, caregivers may use an appropriate personal device (with restrictions) or a dedicated digital device provided by the electronic clinical outcome assessment (eCOA) vendor for the duration of the study.

Two wearable devices will be provided to all caregivers of all participants who are able to walk 10 meters without assistance at screening. These wearable devices record the leg movements of the participant. One device will be worn on each ankle (see Section 8.1.5.12).

[figure not shown]
The equipment will be issued to the caregivers during the screening visit, as will educational materials and an instruction manual. Caregivers will be trained on the correct use of all devices.

All dedicated digital devices must be returned to the clinic *upon completion of study Part 1 for those who do not continue study participation in Part 2, or upon completion of study Part 2, or upon early termination.*

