### 3.2. ASSESSMENT OF CAUSALITY

Investigators should use their knowledge of the participant, the circumstances surrounding the event, and an evaluation of any potential alternative causes to determine whether or not an adverse event is considered to be related to the study treatment, indicating "yes" or "no" accordingly. The following guidance should be taken into consideration:

- Temporal relationship of event onset to the initiation of study treatment.
- Course of the event, considering especially the effects of dose-reduction, discontinuation of study treatment, or reintroduction of study treatment.
- Known association of the event with the study treatment or with similar treatments.
- Known association of the event with the disease under study.
- Presence of risk factors in the participant or use of concomitant medications known to increase the occurrence of the event.
- Presence of non-treatment-related factors that are known to be associated with the occurrence of the event.

For participant receiving combination therapy, causality will be assessed individually for each protocol-mandated therapy.

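### Seizure status is due at the Part 1 Follow-up visit, but as extracted Table 1 ends the seizure diary at Day 365, so off-drug seizure counts have no scheduled diary behind them

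*Combined protocol and SAP*

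**What the plan says.** **Basis of seizure status.** Section 8.2.4 has the investigator determine recent seizure status at the scheduled timepoints "based on caregiver report (time since last visit) and review of the information in the seizure diary". It leaves the look-back windows to another table ("see Table 11 for review period for each assessment"), which is not in the public text. Section 4.2.3.1 describes the eCRF entry as following a review of the diary together with the caregiver.

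**Schedule.** In Table 1 the row "Seizure status" is marked at Baseline, Days 28, 92, 183, 274 and 365, Follow-up (Day 395) and Early Termination. The row "Seizure diary" is an arrow from Screening to Day 365. Footnote q limits the Follow-up visit to participants who stopped Part 1 early or who completed it without entering the extension.

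**Devices.** Section 8.1.3.2 has loaned devices returned on completing Part 1 "for those who do not continue study participation in Part 2, or upon completion of study Part 2, or upon early termination".

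**Use of the data.** Section 9.3.3 analyses seizure change from diary-derived status. Appendix 2, Section 3.2 lists among the considerations for causality: "Course of the event, considering especially the effects of dose-reduction, discontinuation of study treatment, or reintroduction of study treatment".

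**Follow-up monitoring.** The risk mitigations in Section 2.3.1.2 include "safety monitoring throughout the treatment period and follow-up period [laboratory tests, ECG, seizure status, and EEG".

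**The concern.** The protocol treats seizure worsening as a central open safety question. Section 2.3.1.2 says the risk in Dup15q syndrome is not established, and Section 4.1.3 makes clinically relevant worsening an individual stopping criterion. When a child stops, the course over the following weeks is part of the evidence on relatedness. If the on-drug period is diary-recorded and the off-drug period is reported from memory at one visit, the two differ in method as well as in treatment. Under-reporting off drug could pass for improvement after stopping; vague reporting could hide seizures that continue. Adverse event collection does not fill this gap for ordinary seizures, because Section 8.3.7 keeps seizures in line with the participant's history out of adverse event reporting unless they are serious.

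**Working it through.** The plan states no figure to reproduce here. The check is a comparison of schedule rows followed by day arithmetic.

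**Step 1. Rows of Table 1, as extracted (12 visit columns each).**

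| Row | Starts or first marked | Ends or last marked | Follow-up | Early Termination |
|---|---|---|---|---|
| Seizure status | Baseline | Early Termination | yes | yes |
| Seizure diary | Screening | Day 365 | blank | blank |
| Drug diary | Day 1 | Day 365 | blank | blank |
| Adverse events | Screening | Early Termination | covered | covered |
| Concomitant treatments | Screening | Early Termination | covered | covered |
| EEG | Baseline | Day 365 (footnote q) | blank | blank |

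The seizure diary stops in the same column as the drug diary, while two other arrows in the table run to the last column. The shorter span is therefore a difference within one table. Section 8.10 requires assessments to follow the schedule.

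**Step 2. Length of the gap for a completer who does not roll over.** Visit windows are ±7 days at Day 365 and ±10 days at Follow-up.
- Nominal: 395 − 365 = 30 days.
- Shortest: (395 − 10) − (365 + 7) = 385 − 372 = 13 days.
- Longest: (395 + 10) − (365 − 7) = 405 − 358 = 47 days.

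This counts each window from its nominal day. For an early terminator the gap runs from the early termination visit to the follow-up visit; Section 4.1.1 gives the follow-up period as about 4 weeks.

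**Step 3. What else covers the period.** Adverse events are collected for 28 days after the last dose (Section 8.3.1), which is 30 − 28 = 2 days short of the nominal interval. First-ever seizures and new seizure types are events of special interest (Section 8.3.6). Worsening frequency of a pre-existing condition is an adverse event (Appendix 3, Section 8). Habitual, non-serious seizures are not (Section 8.3.7), so their counts, types and durations are what lack a contemporaneous record.

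**Step 4. Who is affected.** The protocol gives neither an early-stopping rate nor a rate of declining the extension. Its 10% (Section 9.1) is the share not evaluable for efficacy. Borrowing it purely as an assumption for early stopping: 90 × 0.10 = 9 children, 6 of them on basmisanil at 2:1. With about 60% having epilepsy (Section 2.2.1): 9 × 0.6 = 5.4, about 3.6 on basmisanil and 1.8 on placebo. Halving or doubling the assumed rate gives 2.7 to 10.8 children with epilepsy. Those who decline the extension would add an unknown number.

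**Step 5. What a 30-day diary would yield per child.** Expected events = rate × 30/28; Poisson relative SE = 1/√(expected). The rates are assumptions with no source in the protocol.

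| Seizures per 28 days | Expected in 30 days | Relative SE |
|---|---|---|
| 2 | 2.1 | 0.68 |
| 4 | 4.3 | 0.48 |
| 8 | 8.6 | 0.34 |

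Clustering of seizures would widen these. The data would help in reading an individual course but would not support a comparison between arms.

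**Step 6. EEG.** The Part 1 EEG row is blank at Follow-up, whereas Table 3 schedules an EEG at the Part 2 Follow-up. Section 2.3.1.2 speaks of follow-up EEG without distinguishing the parts. This is a separate mismatch and does not bear on the diary.

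**The case against.** The strongest reply is that the gap rests on where one arrow ends in a table read from PDF, and that Table 11, which sets the review periods, cannot be seen. In the same extracted table the last ADOS mark falls under Follow-up, which is odd for an on-site assessment at a visit that may be remote, so column positions are not beyond doubt. This stands as a caveat. If Table 11 gives a diary review period for Follow-up, the problem becomes a conflict between Table 11 and Table 1, and it still has to be reconciled.

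A reader might infer more than the documents support in three respects:
- **That all devices go back at Day 365.** No section says so. Return is on completing Part 1, and Section 4.4 defines study completion as including the last scheduled procedure, which for a non-rollover completer is naturally the Follow-up visit. Only early terminators return devices before it. The diary is also a website that caregivers can open on a personal device (Section 8.1.3.1), so device return removes access only for those using a loaned one.
- **That everything about recovery rests on recall.** The diary is itself completed by the caregiver after each seizure, and caregiver report is part of seizure status at every visit. The clinician and caregiver global impression scales, each with a seizure domain, are scheduled at Follow-up and Early Termination. A temporary interruption during Part 1 falls inside the diary period.
- **That the seizure endpoint is compromised.** It concerns 52 weeks of treatment, which the diary arrow spans.

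All three replies hold. They narrow the point but do not remove it: seizure status is still scheduled at Follow-up on a diary-based definition with no diary scheduled behind it.

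**Conclusion.** The point holds in a limited form. As extracted, Table 1 requires a diary-based seizure status at the Part 1 Follow-up visit without scheduling a diary for the interval it covers. For participants who do not enter Part 2, including early terminators, habitual seizure counts, types and durations over roughly 30 off-drug days (13 to 47 with windows) rest on caregiver report alone. Participants who roll over are unaffected in this interval, since Table 3 continues the diary to Day 548.

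The conclusion assumes that the arrow's end was read correctly and that Table 11 does not provide otherwise. The number of children affected is small and cannot be fixed from the protocol. The on-treatment seizure analysis and the primary efficacy analysis are untouched. This is an inexpensive improvement to the evidence for individual causality judgements; it does not threaten the trial's conclusions.

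**What to change.** 1. In Table 1, extend the seizure diary row to the Follow-up visit for participants who do not enter Part 2, including those who terminate early.
2. In Section 8.1.3.2, let early terminators who use a loaned device keep it until that visit, and state that for non-rollover completers return falls at the same visit.
3. Reconcile Table 1, Section 8.2.4 and Table 11, so that the Follow-up status has a stated review period and a matching data source.
4. If on- and off-treatment diary rates are summarised, keep this descriptive or at individual level. A summary by arm is optional and may be nearly empty.
5. Separately, reconcile Section 2.3.1.2 with the blank EEG cell at Part 1 Follow-up in Table 1.

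The cost is about 30 more days of event-driven diary entries for what is expected to be a minority of caregivers, and later return of some loaned devices. No new instrument, visit or procedure is needed for the diary change.

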## **8.2.5        Vital Signs**

Blood pressure, pulse rate, respiratory rate, and body temperature (oral or tympanic) will be recorded at the timepoints specified in the SoA (Section 1.3). Blood pressure, pulse rate, and respiratory rate should be obtained in a quiet room at a comfortable temperature, with the participant's arm unconstrained by clothing or other material. The participant should be asked to remove all clothing that covers the location of cuff placement. All measurements will be obtained from the same arm and, with the appropriate cuff size, using a well-calibrated automatic instrument with a digital readout, throughout the study (the “ideal” cuff should have a bladder length that is 80% and a width that is at least 40% of arm circumference [a length-to-width ratio of 2:1]). The individual should be comfortably in a semi-supine/supine position, with the legs uncrossed.

## **8.2.6        Electrocardiograms**

At each specified timepoint, 12-lead ECG recordings must be obtained in triplicate (i.e., three useful ECGs without artifacts 2 to 3 minutes apart), per the SoA (see Section 1.3). The average of the three readings will be used to determine ECG intervals (e.g., PR, QRS complex [QRS], and QT). Whenever possible, the same brand/model of a standard high-quality, high-fidelity electrocardiograph machine equipped with computer-based interval measurements should be used for each participant. The conditions should be as close as possible to pre-dose timepoints; this includes but is not limited to food intake, activity level, stressors, and room temperature. To minimize variability, every effort should be made that participants be in a resting position for  $\geq 10$  minutes prior to each ECG evaluation. Body position should be consistently maintained for each ECG evaluation to prevent changes in heart rate. Environmental distractions (e.g., television, radio, conversation) should be avoided during the pre-ECG resting period and during ECG recording. ECGs should be performed prior to any scheduled vital sign measurements and blood draws. In some cases, it may be appropriate to repeat abnormal ECGs to rule out improper lead placement as contributing to the ECG abnormality.

For safety monitoring purposes, the investigator or designee must review, sign, and date all ECG tracings. Paper or electronic copies will be kept as part of the participant's permanent study file at the site. If considered appropriate by Roche, ECGs may be analyzed retrospectively at a central laboratory. ECG characteristics, including heart rate, QRS duration, and PR, and QT, will be recorded on the eCRF. QTcB (Bazett's correction; [Phan et al 2015](#)), QTcF (Fridericia's correction), and RR will be recorded on the eCRF.

Both corrections of QTc will be tabulated and analyzed, although, in children, Bazett's formula appears to provide a better correction of the QT. Changes in T-wave and U-wave morphology and overall ECG interpretation will be documented on the eCRF. T-wave information will be captured as normal or abnormal, U-wave information will be

captured in two categories: absent/normal or abnormal. Any medically relevant changes occurring during the study should be recorded in the AE section of the case report form (CRF).

### **8.2.7 Clinical Safety Laboratory Assessments**

Normal ranges for the study laboratory parameters must be supplied to the Sponsor before the study starts. A list of clinical laboratory tests to be performed is provided in [Appendix 4](#), and these assessments must be conducted in accordance with the laboratories process. If analysis is required to be done centrally, the samples and assays should be clearly identified, and instructions may be provided by the central laboratory manual according to the requirements from the SoA (Section [1.3](#)).

At any time, safety laboratory samples will be given priority over any other sample, such that the volume of blood taken at any single timepoint will not exceed 1% of total blood volume, and the volume collected over any 4-week period throughout the study will not exceed 3% of total blood volume, as per recommendations by the European Union. The Investigator must review the laboratory report, document this review, and record any medically relevant changes occurring during the study in the AE section of the CRF. The laboratory reports must be filed with the source documents. Medically relevant abnormal laboratory findings are those that are not associated with the underlying disease, unless judged by the Investigator to be more severe than expected for the participant's condition.

- In the event of unexplained, abnormal, medically relevant laboratory test values, the tests should be repeated immediately and followed up until values have returned to the normal range and/or an adequate explanation of the abnormality is found.
- If such values do not return to normal/baseline within a period judged reasonable by the Investigator, the etiology should be identified and the Sponsor notified.
- If laboratory values from non-protocol–specified laboratory assessments performed at the local laboratory require a change in participant management or are considered medically relevant by the Investigator (e.g., SAE or AE or dose modification), the results must be recorded in the CRF.

Results of clinical laboratory testing will be recorded on the eCRF or be received as electronically produced laboratory reports submitted directly from the local or central laboratory.

Additional blood or urine samples may be taken at the discretion of the Investigator if the results of any test fall outside the reference ranges or clinical symptoms necessitate additional testing to monitor participant safety.

Where the clinical significance of abnormal laboratory results at screening is considered uncertain, screening laboratory tests may be repeated before randomization to confirm eligibility.

Based on continuous analysis of the data in this study and other studies, any sample type not considered critical for safety may be stopped at any time if the data from the samples collected do not produce useful information.

### **8.2.8 Clinical Assessment of Suicidality**

*In Part 1, suicidality will be assessed for participants aged 6 years and above at the time of signing the Informed Consent Form. In Part 2, suicidality will be assessed for participants aged 6 years and above at the time of the assessment. The Investigator or designee will ask the caregiver of participants the following questions adapted from the C-CASA:*

- Suicidal ideation: Has the participant wished he/she were dead or wished they could go to sleep and not wake up?
- Suicidal behavior: Has the participant made a suicide attempt? Has the participant done anything to harm him or herself?
- Self-injurious behavior: Has the participant engaged in non-suicidal self-injurious behavior?

If the Investigator determines that any of these questions can be asked directly to the participant, based on the participant's ability to understand and to react to the questions, then those questions should be directed to the participant; if not, these should be directed to the caregiver. If the answer to any of these three questions is "yes", then the investigator will further evaluate the suicidal risk of the participant.

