**Table 5 Objectives and Endpoints for Part 1 (cont.)**

Objectives	Endpoints
Secondary (cont.)	
Safety (cont.)	

 
To evaluate the tolerability and safety of 52 weeks of treatment with basmisanil
 
	
 
Abnormal changes in EEG recordings compared to baseline with a focus on treatment-emergent epileptiform abnormalities
 
Systolic and diastolic blood pressure and heart rate measurements
 
Suicidality as assessed through questions from selected items adapted from the C-CASA in participants aged 6 years and above
 
Height, weight, head circumference
 
Tanner staging over time (in participants aged 9 years and above)
 

PK	

 
To characterize the PK of basmisanil and its metabolite M1 [REDACTED]
 
To evaluate potential relationships between selected covariates and exposure to basmisanil
 
	
 
Plasma concentration of basmisanil and its major metabolite M1 at specified timepoints.
 
PK parameters for basmisanil: <math>AUC_{\text{tau,ss}}</math>, <math>C_{\text{max,ss}}</math>, <math>C_{\text{trough,ss}}</math>, <math>CL/F</math>, <math>Vd/F</math>
 
Plasma concentration ratio of M1 to basmisanil at trough
 
PK parameters for M1: <math>C_{\text{max,ss}}</math>, <math>C_{\text{trough,ss}}</math>
 
Other PK parameters as appropriate
 

PD	

 
To evaluate the effects of basmisanil treatment on the characteristic Dup15q EEG phenotype acutely and at steady state
 
	
 
qEEG beta-band power
 

$AUC_{\text{tau,ss}}$  = area under the concentration–time curve during one dosing interval at steady state;  
 C-CASA = Columbia Classification Algorithm for Suicide;  $CL/F$  = apparent clearance;  $C_{\text{max,ss}}$  = maximum concentration at steady state;  $C_{\text{trough,ss}}$  = trough plasma concentration at steady state;  
 PD = pharmacodynamics; PK = pharmacokinetics; qEEG = quantitative EEG;  $Vd/F$  = apparent volume of distribution.

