## Other Exclusions

9. Significant risk for suicidal behavior, as assessed through the suicidal behavior question adapted from the Columbia Classification Algorithm for Suicide Assessment (C-CASA) (participants  $\geq$  6 years of age only).
10. Known sensitivity to any of the study treatments or components thereof, or drug or other allergy that, in the opinion of the Investigator, contraindicates the participation in the study, including severe lactose intolerance (e.g., unable to tolerate 250 mL [8 oz. or 1 cup] of milk, ice cream, or yogurt).
11. Concomitant clinically relevant disease or condition or any clinically significant finding at screening that could interfere with, or for which, the treatment might interfere with, the conduct of the study or that would pose an unacceptable risk to the participants in this study.
12. Known active or uncontrolled bacterial, viral, or other infection (excluding fungal infections of nail beds) or any major clinically significant episode of infection or hospitalization (relating to the completion of the course of antibiotics) within 6 weeks prior to the start of drug administration.

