### **7.1 DISCONTINUATION OF STUDY TREATMENT**

For data to be collected at the time of treatment discontinuation and follow-up and for any further evaluations that need to be completed see the SoA (Section 1.3).

Reasons for discontinuation of study treatment may include, but are not limited to, the following:

- Any medical condition that the Investigator or Sponsor determines may jeopardize the participant's safety if he or she continues study treatment.
- Investigator or Sponsor determination that treatment discontinuation is in the best interest of the participant.
- Participant suicidal behavior or active suicidal ideation with specific plan and intent.

- An event that meets the stopping criteria (see Section 4.1.3).
- Pregnancy.
- Specific AEs if discontinuation of study treatment is required to manage the event (see Section 8.3.8).
- Symptomatic participants with moderate or severe COVID-19 infection (as per WHO guidelines) with signs of pneumonia or hypoxia.

Every effort should be made to obtain information on participants who discontinue study treatment but have not withdrawn consent. Participants who discontinue study treatment prematurely (*Part 1 or Part 2*) will be asked to return to the clinic for a study early termination visit (see Section 8.10.3) and *will be asked to complete the follow-up visit* (see Section 8.10.4), unless the participant withdrew consent. The primary reason for premature study treatment discontinuation should be documented on the appropriate eCRF.

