### **9.3.3 Safety Analyses**

All safety analyses will be based on the safety analysis population. Safety endpoints will be described in appropriate summary tables and graphs. Individual outputs will be presented if required.

Descriptive summaries of exposure to study treatment will be prepared by treatment group (including treatment duration, total dose received, dose intensity).

Verbatim AE terms recorded in the eCRF will be mapped to MedDRA thesaurus terms. AE severity will be graded according to National Cancer Institute Common Terminology Criteria for AEs (v5.0). Data on AEs, SAEs, and deaths will be presented by treatment group in summary tables and in individual outputs, as appropriate.

Abnormal changes in EEG recordings compared to baseline will be presented in summaries and individual outputs with a focus on treatment-emergent epileptiform abnormalities. Seizure status as derived from the seizure diary entries by caregivers will be used to analyze changes from baseline in seizure types, frequency, and duration.

All clinical laboratory data will be stored on the database in the units in which they were reported. Laboratory test values will be presented in International System of Units (Système International d'Unités [SI] units;). Individual outputs will show flags for abnormal results. Summaries and shift tables will be prepared for selected laboratory tests to describe baseline and maximum post baseline severity grade.

Vital sign data will be presented *by individual listings* with flagging of values outside the normal ranges and flagging of abnormalities.

ECG data as well as data for height, weight, and head circumference will be presented using appropriate summaries and/or listings.

Suicidality questions adapted from the C-CASA will be analyzed descriptively in *participants aged 6 years and above*.

Tanner staging over time will be described in *participants from age 9*.

**Concomitant Medications:** The original terms recorded on the participants' eCRF by the Investigator for concomitant medications will be standardized by the Sponsor by utilizing a mapped term and appropriate drug dictionary level. Concomitant medications will be presented using appropriate outputs.

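### The suicidal-behavior question in Section 8.2.8 has no intent qualifier or recall period, so the suicidality safety endpoint can record non-suicidal self-injury as suicidal behavior

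*Combined protocol and SAP*

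**What the plan says.** Section 8.2.8 has the investigator or a designee put three items to the caregiver, or to the participant when judged able to answer. The first concerns suicidal ideation. The second is "Suicidal behavior: Has the participant made a suicide attempt? Has the participant done anything to harm him or herself". The third is "Self-injurious behavior: Has the participant engaged in non-suicidal self-injurious behavior". If any of the three is answered yes, "then the investigator will further evaluate the suicidal risk of the participant".

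These items serve as a safety endpoint. Table 5 lists "Suicidality as assessed through questions from selected items adapted from the C-CASA" for participants aged 6 and above, and Table 6 repeats it for Part 2. The planned analysis in Section 9.3.3 is one line: "Suicidality questions adapted from the C-CASA will be analyzed descriptively".

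Related wording appears in two other places. Exclusion criterion 9 in Section 5.2 reads "Significant risk for suicidal behavior, as assessed through the suicidal behavior question adapted from the Columbia Classification Algorithm for Suicide Assessment". Section 7.1 lists, among possible reasons for stopping study treatment, "Participant suicidal behavior or active suicidal ideation with specific plan and intent".

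**The concern.** The item headed suicidal behavior contains two different probes that share one answer. The first asks about a suicide attempt. The second asks about any self-harm, whatever its purpose. A child who bites a hand with no wish to die gives a truthful yes to the second probe, and therefore to the item, and another truthful yes to the self-injury item. The recorded data then do not distinguish that child from one who made an attempt and also self-injures.

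The missing time window adds to this. Other instruments in the plan state one: the past week for the sleep questionnaire (Section 8.1.5.10), 7 days for the family impact module (Section 8.1.5.6), and the time since the last visit for seizure status (Section 8.2.4). The suicidality items state none, although they are asked repeatedly.

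At stake is how far a descriptive safety endpoint can be interpreted. Section 8.3.8 calls suicidality monitoring mandatory for CNS-active drugs. If the item picks up mainly self-injury without intent, its table says little about suicidal behavior. Analysts cannot repair this later, because intent that was not recorded at the visit cannot be derived afterwards.

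**Working it through.** The plan states no figure on this point, so there is none to reproduce. The check is a truth table of the wording, followed by an illustrative count.

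**Truth table, items read literally.** The suicidal-behavior item is yes if either probe is yes.

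| Suicidal act | Non-suicidal self-injury | Suicidal-behavior item as worded | Same item if intent were required | Self-injury item |
|---|---|---|---|---|
| no | no | no | no | no |
| no | yes | **yes** | no | yes |
| yes | no | yes | yes | no |
| yes | yes | yes | yes | yes |

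Under the literal reading, every yes on the self-injury item implies a yes on the suicidal-behavior item. The pattern that should identify self-injury alone (no on the second item, yes on the third) does not arise.

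**How many are asked.** About 90 participants are randomized, and Section 4.1 aims for at least about one-third aged 2 to 5 years. Part 1 assesses those aged 6 or above at consent: 90 × (1 − 1/3) = 60 at most, approximately.

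**How many could be affected.** Let s be the share with non-suicidal self-injury and t the share with true suicidal behavior. The documents give neither. Both are assumed, and they are treated as independent. The probability of a yes is t + s − t·s. With t = 0, the count is 60 × s, and every one of these would be no if intent were required.

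| Assumed s | Yes on suicidal-behavior item | Specificity (1 − s) | Positive predictive value at assumed t = 1% |
|---|---|---|---|
| 5% | 3 | 95% | 0.01/0.0595 = 17% |
| 10% | 6 | 90% | 0.01/0.109 = 9% |
| 20% | 12 | 80% | 0.01/0.208 = 5% |
| 30% | 18 | 70% | 0.01/0.307 = 3% |
| 50% | 30 | 50% | 0.01/0.505 = 2% |

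**How often a past act can recur.** Table 1 schedules the assessment at screening, baseline, Day 2 and Days 28, 92, 183, 274 and 365. That is six post-baseline occasions up to Day 365. A follow-up assessment comes later for those who do not enter Part 2, and contacts at least every 3 months for those who do. With no recall window, one earlier act can be answered yes on each occasion.

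**Whether anything downstream corrects the answer.** Section 8.2.8 requires evaluation of risk after a yes, but says nothing about changing the answer. Table 5 defines the endpoint by the questions, and Section 9.3.3 summarizes the questions. Neither section states adjudication, a derivation rule or a comparison with baseline.

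**The case against.** The strongest reply is that the intended split is visible. The item is headed suicidal behavior, the third item says non-suicidal, and Section 8.1.4.1 has a clinician complete the questions. A careful rater can apply the distinction. Section 8.1.4 also refers to a separate Rater Manual, which may cover intent and recall, although the protocol does not say that it covers these items. This stands as far as it goes: the endpoint can misclassify, but it need not. It does not remove the point, because the literal wording allows the double count and no visible rule prevents it.

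A second reply is that a broad probe followed by clinical evaluation is a sound way to screen. That holds for protecting the participant, but it does not clean the recorded endpoint. It also warns against a careless remedy. Sending all self-harm without identifiable intent to the non-suicidal item would hide ambiguous events in children who can rarely report intent.

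A third reply is that Part 1 is randomized and placebo-controlled, that the items are asked at screening and baseline, and that an actual attempt would also be reportable as an adverse event. This also stands. A reader might infer that the wording will produce a false signal against basmisanil or bury a real event, but the documents do not support so strong a claim. Background self-injury is expected in both arms, and prior positives are identifiable.

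A reader might also infer that a child with stable self-injury would be excluded or taken off treatment. The text does not say so. Exclusion criterion 9 requires a significant risk. Section 7.1 lists reasons that may apply and does not cite the question.

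Finally, a reader might infer that the protocol describes self-injury as common in this syndrome. It does not. Section 2.2.1 does not name self-injury among the challenging behaviors, and Section 8.1.5.8 only describes a standard subscale of a repetitive-behavior questionnaire.

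**Conclusion.** The concern holds as a measurement ambiguity that should be fixed. As worded, one non-suicidal act can be positive on two items, and a past act can be positive at every visit. Nothing visible re-codes the answer before it enters the descriptive suicidality endpoint in Part 1 or Part 2.

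The size cannot be taken from the documents. The 3 to 30 children rest on an assumed self-injury rate of 5% to 50%, on at most about 60 assessed participants, and on raters following the literal text. Raters who apply the implied split would produce fewer. The predictive values rest further on an assumed 1% rate of true suicidal behavior. The endpoint is descriptive, and the primary efficacy analysis is not affected.

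**What to change.** In Section 8.2.8 and on the form:

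- Record the two probes of the suicidal-behavior item separately.
- Add an intent field with three responses: suicidal intent, no suicidal intent, cannot be determined. The third response keeps ambiguous acts visible instead of defaulting them to non-suicidal.
- After baseline, ask about the period since the last visit.

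In Section 9.3.3, tabulate suicidal behavior, self-harm of undetermined intent and non-suicidal self-injury as mutually exclusive categories by arm, showing those new or worsened since baseline. Because the items are yes or no, the table shell must say what counts as worsened. The Part 2 summaries should use the same categories.

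Exclusion criterion 9 and the Section 7.1 reason should be reconciled with Section 8.2.8, so that it is clear which recorded category each refers to. No clinical rule is proposed here.

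The cost is a small form change and one table shell, with no added visits. The form change should come early, because answers already collected cannot be reclassified by intent.
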